7.5.2. Outcome measures completed by parents/ guardians

The parents/guardians will complete a range of questionnaires aiming to measure parental perspectives of their child with autism. Before completing baseline measures, the parents/ guardians will be asked to complete the Social Communication Questionnaire (SCQ) to

establish the child's eligibility for the trial; if the SCQ score is 15 or above the child will be eligible for the trial. The parent/ guardian will then be asked to complete a demographic questionnaire pertaining to the child and the parent. Demographic information will be collected using a novel demographic information form and will include questions focusing on the child's clinical ASD diagnosis (such as: name and profession of the person who made the ASD diagnosis, date of diagnosis, assessment type, and whether there is an official diagnosis letter).

Parents/ guardians will also be asked to complete the Social Skills Improvement System, Strengths and Difficulties Questionnaire (SDQ) (Goodman, 1997) to measure the participating child's emotional and behavioural difficulties. Lastly, the EQ-5D (3L proxy version) (The EuroQol Group, 1990) and a bespoke resource use questionnaire will be completed to assess the child's health-related quality of life and to capture the healthcare and non-health resource implications (including costs in the education sector, costs of productivity loss and out-of-pocket expenditures for parents) attributable to the child's difficulties due to their condition. Parents/guardians will also be asked to complete a bespoke questionnaire to assess the acceptability of the intervention to their children (in the intervention group only).

7.5.3. Outcome measures completed by the associated teacher/ TA

At baseline, the associated teacher/ TA to the participating child will be asked to complete the Social Skills Improvement System, the SDQ, and a bespoke resource use questionnaire. The SDQ and the resource use questionnaires will pertain to the participating child and will capture any emotional and behavioural difficulties and the resource implications of the child's behaviour at school. The associated teacher/ TA will also be asked to complete some questions to assess any adverse events that may have been attributable to the intervention.

7.5.4. Outcome measures completed by the interventionist teacher/ TA

At baseline, the interventionist teacher/ TA will be asked to complete a small demographic questionnaire including information such as their role in the school, how long they have worked in an educational setting, and whether they have run LEGO®-based therapy groups previously. After each LEGO®-based therapy session the interventionist teacher/ TA will be asked to complete a fidelity checklist, a bespoke resource use questionnaire to capture the resource implications of running the LEGO®-based therapy groups at school, a custom designed questionnaire to assess any adverse events that may have been attributable to the intervention, and an acceptability questionnaire. In addition to this, acceptability will be further assessed through qualitative interviews, conducted by telephone with a purposive sample of 20% of the intervention ists across school types (primary/secondary and sociodemographic variables) post-intervention (n=12).

7.6. Blinding

The trial statisticians will remain blind throughout the duration of the study period. The DMEC will have access to the unblinded data at their request during the trial, for example if they are concerned of potential harm caused by the intervention; this data will be prepared by the data management team in the CTRU, aided by another CTRU statistician when required. Both trial statisticians will be blind to group allocation at each phase of the trial.

Research assistants collecting outcome data will be blinded to the trial treatment. Instances of unblinding will be recorded using a bespoke unblinding form (which will include information on who was unblinded, the source of unblinding, and the reason for unblinding). All measures are self report and children, parents and teachers will be aware of the treatment allocation for the trial.

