Trial Design	Pragmatic, cluster randomised controlle	ed trial with internal pilot	
Trial Participants	Children diagnosed with autism spectru	ım disorder (ASD)	
Planned Sample Size	240		
Intervention duration	12 weeks		
Follow-up duration	12 months after randomisation		
Planned Trial Period	4 years	_	
	Objectives	Outcome Measures	
Primary (20 weeks)	To examine the clinical effectiveness of LEGO®-based therapy groups on the social and emotional competence (specifically the perceived social skills) of children with ASD within the school setting, when compared with usual support provided for children with ASD.	The social skills subscale of the Social Skills Improvement System (SSIS) – completed by the associated teacher at 20 weeks(NB: The Social Skills Improvement System (SSIS) is also completed by the associated teacher at baseline and 52 weeks and by the parent at baseline, 20 and 52 weeks. This is a secondary outcome.)	
Secondary (20 and 52 weeks)	1. Examine the clinical effectiveness of LEGO®-based therapy groups on the perceived social isolation of children with ASD within the school setting, when compared with usual support provided.	Multidimensional Scale of Perceived Social Support – completed by the child at baseline, 20 and 52 weeks. Asher loneliness scale – completed by the child at baseline, 20 and 52 weeks.	

2. Examine the cost-effectiveness of LEGO®-based therapy groups in terms of health-related quality of life and cost utility at 20 and 52 weeks.	EQ-5D-Y proxy – completed by the parent at 20 and 52 weeks. Child Health Utility 9D (CHU-9D) – completed by the child at 20 and 52 weeks.
	Bespoke resource use questionnaire – completed by the parent and associated teacher at 20 and 52 weeks.
3. Determine if the impact of LEGO-®- based therapy is sustainable into the next academic year by comparing effectiveness on social and emotional competence (specifically perceived social skills) at 20 and 52 weeks after randomisation.	The social skills subscale of the Social Skills Improvement System (SSIS) – completed by the associated teacher at 20 and 52 weeks and compared between these time-points.
4. Examine the acceptability of the intervention at follow-up points using a purpose designed questionnaire and telephone interviews.	Bespoke acceptability questionnaire – completed by the parent and interventionist at 20 weeks (intervention group only).

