3.2. Secondary Objectives

The secondary objectives of this trial are to:

- Examine the clinical effectiveness of LEGO®-based therapy groups on the perceived social isolation of children with ASD within the school setting when compared with usual support provided. This is measured using the Multidimensional Scale of Perceived Social Support and the Asher Loneliness scale completed by the child at baseline, 20 and 52 weeks.
- Examine the cost-effectiveness of LEGO®-based therapy in terms of health-related quality of life and cost utility at 20 and 52 weeks. This is measured using the parent completed EQ-5D-Y proxy and bespoke resource use questionnaire, and the child completed Child Health Utility 9D (CHU-9D) at 20 and 52 weeks.
- 3. Determine if the impact of LEGO®-based therapy is sustainable into the next academic year by comparing effectiveness on social and emotional competence (specifically perceived social skills) at 20 and 52 weeks. This is measured using the social skills subscale of the SSIS completed by the associated teacher at 20 and 52 weeks and a comparison between them.
- 4. Examine the acceptability of the intervention at follow-up points using a bespoke purpose designed questionnaire and telephone interviews. This is measured with the parent and interventionist completed bespoke acceptability questionnaire at 20 week (intervention group only).
- 5. Examine treatment fidelity through independent observation of treatment sessions across schools. This is measured using the fidelity checklist completed by the interventionist after each LEGO®-based therapy session.
- 6. Examine the clinical effectiveness of LEGO®-based therapy groups on the academic competence of children with ASD within the school setting, when compared with usual support provided for children with ASD. This is measured with the academic competence subscale of the SSIS completed by the associated teacher at baseline, 20 and 52 weeks.
- 7. Examine the emotional and behavioural symptoms in those receiving LEGO®-based therapy compared to usual care. This is measured using the Strengths and Difficulties Questionnaire (SDQ) and the problem behaviours subscale of the SSIS completed by the parent and associated teacher at baseline, 20 and 52 weeks.

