Bespoke resource use questionnaire	20 weeks after randomisation	Research assistant/post/ online form
	52 weeks after randomisation	Research assistant/post/ online form
Bespoke adverse events questionnaire	20 weeks after randomisation	Research assistant
	Baseline	Research assistant
EQ-5D-Y (3L proxy)	20 weeks after randomisation	Research assistant/post/ online form
	52 weeks after randomisation	Research assistant/post/ online form
Bespoke acceptability questionnaire	20 weeks after randomisation	Research assistant/post/ online form
(intervention group only)		

Table 2: Outcome measures to be completed by parents throughout the I-SOCIALISE trial

Time points completed	Administered by
Baseline	Research assistant
20 weeks after randomisation*	Research assistant/post/ online form
52 weeks after randomisation	Research assistant/post/ online form
Baseline	Research assistant
20 weeks after randomisation	Research assistant/post/ online form
52 weeks after randomisation	Research assistant/post/ online form
Baseline	Research assistant
20 weeks after randomisation	Research assistant/post/ online form
52 weeks after randomisation	Research assistant/post/ online form
20 weeks after randomisation	Research assistant/post/ online form
	Baseline 20 weeks after randomisation* 52 weeks after randomisation Baseline 20 weeks after randomisation 52 weeks after randomisation Baseline 20 weeks after randomisation 52 weeks after randomisation 52 weeks after randomisation

Table 3: Outcome measures to be completed by associated teacher/teaching assistant throughout the I-SOCIALISE trial

*Primary Outcome

Measure	Time points completed	Administered by
Demographics	Baseline	Research assistant
Bespoke acceptability questionnaire	20 weeks after randomisation	Research assistant

Table 4: Outcome measures to be completed by interventionist teacher/teaching assistant throughout the I-SOCIALISE trial

Table 5: Recording details of the intervention

Measure	Time points completed	Administered by
Bespoke resource use questionnaire	After each therapy session	Interventionist
Bespoke adverse events questionnaire	After each therapy session	Interventionist
Fidelity checklist	After each therapy session	Interventionist

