7.5.1. Outcome measures completed by children and young people

The child participants will complete a small series of self-report questionnaires at all time points during the study. Although the main focus will be on the child or young person completing these measures, a research assistant (RA) and parent/guardian will be on hand to assist if the child is having difficulties completing questionnaires (e.g. not understanding a question). Two of the three questionnaires the child participants will be asked to complete are pertinent to understand their perceived social isolation. The Asher Loneliness Scale (Asher, Hymel, & Renshaw, 1984) and the 8 items relating to support from friends and a significant other (within the school setting) in The Multidimensional Scale of Perceived Social Support (Zimet, Dahlem, Zimet, & Farley, 1988)will be used to assess perceived social isolation. Lastly, the child participants will be asked to complete the Child Health Utility 9D (CHU-9D) (Stevens, 2011) to assess the child's health-related quality of life.

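### Section 7.6 calls outcome-collecting research assistants blinded, but Tables 2 and 4 give research assistants two 20-week forms that exist only in the intervention arm, and nothing keeps the two tasks apart

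*Protocol*

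**What the plan says.** - **Blinding (Section 7.6).** "Research assistants collecting outcome data will be blinded to the trial treatment". No exception is made and no unblinded assistant is named. The section adds: "Instances of unblinding will be recorded using a bespoke unblinding form". It also says that all measures are self-report and that children, parents and teachers know the allocation.
- **Acceptability forms.** The synopsis and Section 3.2 (objective 4) give a 20-week questionnaire to the parent and to the interventionist and restrict it: "intervention group only". Section 7.5.2 repeats the restriction for parents.
- **Who administers them (Section 4).** Table 2 lists the parent form as given by research assistant, post or online form. The table captioned "Table 4: Outcome measures to be completed by interventionist teacher/teaching assistant" lists the interventionist form at 20 weeks with the research assistant as the only mode.
- **Who collects outcomes.** Section 7.5 gives data collection to a trained research assistant. Tables 1 to 3 offer research assistant, post or online for the 20- and 52-week outcome measures. For the child measures, Section 7.5.1 says: "a research assistant (RA) and parent/guardian will be on hand to assist if the child is having difficulties completing questionnaires".
- **Primary outcome (Section 4.1).** The teacher-completed SSIS social skills subscale is openly declared unblinded.

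**The concern.** All respondents know the allocation, so the blinded research assistant is the only masking left in outcome collection. The schedule gives that same staff role a task that reveals the arm, at the time point when outcomes are collected. If the assistant knows the arm, help given to children who struggle with the loneliness, social support and CHU-9D measures could differ between arms. Those measures serve secondary objectives 1 and 2. A report that repeats Section 7.6 as it stands would also describe a masking that the schedule does not protect.

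**Working it through.** No arithmetic decides this point. It rests on setting the 20-week schedule beside the blinding statement.

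| Form at 20 weeks | Arm | Mode listed | Source |
|---|---|---|---|
| Child loneliness, social support, CHU-9D | both | assistant, post, online | Table 1 |
| Parent SSIS, SDQ, EQ-5D-Y, resource use | both | assistant, post, online | Table 2 |
| Associated teacher measures, including the primary outcome | both | assistant, post, online | Table 3 |
| Parent acceptability | intervention only | assistant, post, online | Table 2 |
| Interventionist acceptability | intervention only | assistant | Table 4 |
| Parent adverse-event questions | both | assistant | Table 2 |

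1. **Same role, same time point.** Both acceptability forms fall at 20 weeks, and both list the role that collects the outcomes.
2. **The forms reveal the arm.** The interventionist delivers the therapy, so that form has no counterpart in the control arm. The parent form is restricted to the intervention arm in plain terms.
3. **Absence is informative too.** If assistants carry the form only to intervention families and schools, having none to carry points to control. Both arms are exposed.
4. **The cluster design spreads the information.** Section 7.4.1 randomises schools, so one form reveals the arm of every trial child in that school.
5. **No safeguard is written.** Nothing assigns these forms to separate staff or places them after the outcome measures. Section 10.7 does declare an unblinded team member for the qualitative interviews, but no such statement covers the acceptability forms. The unblinding form records events and does not prevent those that the schedule creates.
6. **Scale.** Section 10.1 plans 120 children per arm. The share of families seen face to face is not given, so assistant-delivered parent forms could relate to anywhere from 0 to about 120 children. Section 7.8 treats 12 interventionists as 20%, which implies 12 / 0.20 = 60 interventionists. On Table 4 as written, all of these forms go through an assistant. These are ceilings on exposure, not estimates of how many assistants become unblinded.
7. **Another route.** Table 2 lists the parent adverse-event questions as given by the research assistant only. Section 4.2.2 says they ask about events attributable to the trial intervention or to usual care, so the answers can disclose the arm. Moving the acceptability forms alone would leave this route open.

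**The case against.** **The tables name a role, not a person.** One assistant could hand over the acceptability form and another collect outcomes at that school. The team already has unblinded members: trial managers tell schools their allocation (Section 7.4.2), and research team members may train interventionists (Section 8.1) and watch session videos (Section 8.3.2). This stands. A reader might infer that the blinding cannot hold at all, but the documents do not support that. Blinding fails only where the same assistant handles the form and collects outcomes at that school. The protocol permits this and does nothing to prevent it.

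**Other modes exist.** The parent form can go by post or online, and Section 7.5 allows online follow-up for teachers and TAs, which could be read to include interventionists. Outcomes might also be taken first. This reduces exposure, but Table 4 lists no alternative mode and no order is set.

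**Unblinding is logged.** This supports honest reporting, so it does not follow that the final report must misstate the blinding. It leaves the cause in place.

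**The impact is small.** This largely stands. The assistant is not a rater, and help is given only when a child has difficulty, with a parent who knows the allocation also on hand. The child measures may also be completed by post or online. A reader might infer bias in the primary outcome, but that is a teacher's report already declared unblinded. An effect at 52 weeks requires the same assistant to return, which the protocol does not state.

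**Section 7.5.4 times the interventionist form differently.** It places the form after each session, whereas the synopsis, Sections 3.2, 4.2.4 and 7.8 and Table 4 place it at 20 weeks. The single divergent sentence should be reconciled, but it does not remove the assistant from Table 4.

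**Conclusion.** The concern holds as an inconsistency that should be corrected. Section 7.6 claims blinding without exception, while Tables 2 and 4 give the same staff role two forms that disclose allocation, with no separation of people or order. Both arms are affected. It would be wrong to conclude that only intervention visits are exposed, since absence of the form signals control, or that some 120 families will unblind an assistant, since that figure is only the planned arm size.

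The likely bias is modest and cannot be quantified from the protocol. It lies mainly in child-completed secondary measures where an assistant helps, at 20 weeks and conditionally at 52 weeks. This rests on two assumptions: that the schedule is followed as written, and that at least some assistants do both tasks at the same school. The primary analysis is not materially affected.

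**What to change.** - In Tables 2 and 4, make both acceptability questionnaires post or online only, sent by the trial managers, who already know the allocation, after the 20-week outcome booklets have been collected.
- In Section 7.6, state that assistants who collect outcomes do not handle forms that exist in one arm only.
- Take the parent adverse-event questions after the child measures at the 20-week visit. This protects the 20-week child measures; any disclosure should still be logged, because it carries over to 52 weeks if the same assistant returns.
- Align Section 7.5.4 with the 20-week timing given elsewhere for the interventionist form.
- Where collection has already taken place without these steps, qualify the blinding statement in Section 7.6 and report the logged unblinding by arm.

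The cost is small: a change of mode for two forms, using routes already in place, and a change of order at one visit. The downside is that response to the acceptability questionnaires may be slightly lower.

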7.7. Withdrawal criteria

Withdrawal can occur at any point during the study at the request of the participants or schools.

Where a parent wishes to withdraw from the study, withdrawal will be clarified by establishing whether they wish for their child to be withdrawn or if they themselves wish to withdraw. Where withdrawal is only for the participating parent, the child may continue to take part in all aspects of the trial.

Where an interventionist wishes to withdraw, withdrawal will be clarified as whether the school wishes to withdraw or they themselves wish to withdraw. Where withdrawal is only for the interventionist, attempts will be made to replace them for the intervention period.

If a child or their associated teacher/TA or school indicates that they wish to withdraw from the study or the parent wishes to withdraw their child from the study, withdrawal will be clarified by establishing whether the withdrawal is from the intervention, from follow-up or from all aspects of the study. Where withdrawal is only from the intervention then follow-up data will continue to be collected. Data will be retained for all participants up to the date of withdrawal, unless they specifically request for their data to be removed. We will provide an opportunity for all those who withdraw or indeed who choose not to give informed consent to have a chance to explain why they have decided to not continue participation.

Where a teacher withdraws consent we will consent another associated teacher if appropriate. If another teacher completes the questionnaires at follow-up points without the consented teacher formally withdrawing, this will be taken as implied consent to use that data and we will not collect further data from this teacher (e.g. contact details).

In the event that a child is found to be ineligible when basline data is taken, i.e. they do not have a confirmed diagnosis of Autism and/or they score >15 on the SCQ, they will be withdrawn from the study and will not be included in the ITT analysis.

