4.2.2. Parent questionnaires

- The Social Communication Questionnaire (SCQ) (Rutter, Bailey, & Lord, 2003) is a parent completed questionnaire derived from the Autism Diagnostic Interview–Revised (Lord, Rutter, & [name], 1994). The recommended cut-off to suggest it is likely an individual has ASD is 15. The SCQ has excellent sensitivity and reliability (Chandler et al., 2007). It will only be completed as an eligibility check prior to baseline – *baseline only*.
- 2. The Social Skills Improvement System (SSIS) (Gresham & Elliott, 2008) (further details in section 4.1).
- 3. Demographic information pertaining to the child and the parent will be collected. This will be done using a novel demographic information form *baseline only*.
- 4. The Strengths and Difficulties Questionnaire (SDQ) (Goodman, 1997), consisting of 25 items, will be used to measure the participating child's emotional and behavioural difficulties, distress and social impairment. Participating parents will mark a 3 point scale indicating if each statement is true, somewhat true, or certainly true (e.g. considerate of other people's feelings). This is an internationally recognised reliable and valid measure used in studies of children & adolescents including those with ASD.
- 5. The EQ-5D-Y (3L proxy version) (The EuroQol Group, 1990) is a five item generic preference-based measure of health-related quality of life that allows a proxy person to complete the measure for the participant. The use of this measure allows for the comparison between groups across a wide range of comparable dimensions and can therefore be used to perform a cost-utility analysis.
- 6. Bespoke resource use questionnaires, as described above, to capture the healthcare and non-health resource implications (including costs in the education sector, and costs of productivity loss and out-of-pocket expenditures for parents) attributable to the child's difficulties due to their condition.
- 7. Bespoke questionnaire to assess acceptability of the intervention 20 weeks only.
- 8. Custom designed questions (included in resource use form at 20 weeks) to assess any adverse events that may have been attributable to the trial intervention or usual care interventions. This will be developed in conjunction with our PPI representatives and the local authorities *20 weeks only*.

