6.1. Inclusion criteria

A participant will be included if the child:

- Is aged between 7 and 15 years at the time of randomisation of the school (based on previous research and extensive PPI recommendations).
- Attends a mainstream school in years 2-10.
- The child and parent/ guardian have a sufficient understanding of English to be able to provide informed consent and read the LEGO®-based therapy instructions.
- Has an ASD clinical diagnosis from a qualified assessing clinician or team [based on bestpractice guidance leading to an ICD-10 (World Health Organization, 1993) or DSM-IV diagnosis (American Psychiatric Association, 2000) as reported by the child's parent/ guardian and in the child's school records (this may include the school's special educational needs (SEN) register, an individual education plan (IEP), individual health care plan, my support plan (MSPs), education health care plans (EHCPs), individual learning plans (ILP's) or equivalent).
- Scores 15 or higher on the Social Communication Questionnaire.
- Has the ability to follow and understand simple instructions (as determined by the associated teacher/ TA or parent/ guardian).

A school will be included if:

- It is a mainstream school located in Leeds, York, Sheffield or surrounding areas in the North of England.
- It has not used LEGO®-based therapy with the child in the current or preceding school term. For research purposes, LEGO®-based therapy is defined as meeting all of the main fidelity checklist criteria.
- They have at least one child diagnosed with ASD (in line with child inclusion criteria above)

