7.2. Screening and Eligibility Checks

Research assistants will contact all families who have expressed an interest in taking part in the trial by telephone to screen participants for eligibility for the I-SOCIALISE trial. Firstly, we will ascertain that child meets the following criteria:

- Is aged between 7 and 15 years at the time of randomisation of the school (based on previous research and extensive PPI recommendations)
- Attends a mainstream school in years 2-10.
- Has an ASD clinical diagnosis from a qualified assessing clinician or team [based on bestpractice guidance leading to an ICD-10 (World Health Organization, 1993) or DSM-IV diagnosis (American Psychiatric Association, 2000)] as reported by the parent/guardian.
- Scores 15 or higher on the Social Communication Questionnaire (this will be completed at the first visit).
- Has the ability to follow and understand simple instructions (as determined by the associated teacher/ TA or parent/ guardian).

If a child appears eligible for inclusion after confirming a diagnosis of ASD with parents / guardian over the phone, the research assistant will arrange a face-to-face visit in order to take full informed consent, confirm eligibility and take baseline measures. The parent will be asked to complete the Social Communication Questionnaire on behalf of the child; those who score 15 or higher on the SCQ will be included in the trial. Any child or young person who does not meet the eligibility criteria for study participation and/or do not consent to the trial will be signposted to alternative sources of help relevant to their local area.

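### Section 7.7 states the SCQ threshold in the wrong direction: the rule that withdraws ineligible children and excludes them from the ITT analysis names scores above 15, which the protocol elsewhere makes eligible

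*Protocol*

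**What the plan says.** The protocol gives the SCQ entry threshold three times, always in the same direction:

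- Section 6.1 (inclusion criteria): "Scores 15 or higher on the Social Communication Questionnaire".
- Section 7.2 (screening): "those who score 15 or higher on the SCQ will be included in the trial".
- Section 7.5.2 (parent measures): "if the SCQ score is 15 or above the child will be eligible for the trial".

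Section 4.2.2 explains the direction of the scale: "The recommended cut-off to suggest it is likely an individual has ASD is 15". Higher scores point towards ASD, so a lower limit of 15 suits a trial in children with ASD.

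Section 7.7 (withdrawal criteria) then deals with a child who turns out to be ineligible at the time baseline data are taken. It spells out what ineligible means: "they do not have a confirmed diagnosis of Autism and/or they score >15 on the SCQ". The SCQ condition and its consequence, read together, are: "they score >15 on the SCQ, they will be withdrawn from the study and will not be included in the ITT analysis".

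**The concern.** Section 7.7 should describe the children who fail the inclusion criteria. On the SCQ it describes those who pass. Because the two conditions are joined by and/or, the SCQ condition is sufficient on its own: a child with a confirmed diagnosis and a score of 16 meets it.

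The sentence matters because it settles who is withdrawn and who is left out of the ITT analysis. Section 10.2 applies ITT to all outcome measures but neither repeats nor corrects the SCQ condition. Anyone deriving the analysis population from section 7.7 would be working from a reversed criterion.

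**Working it through.** No figure in the protocol depends on this rule, so there is nothing to reproduce. The check is logical. An inclusion rule and an ineligibility rule based on the same score are coherent only if every score falls under exactly one of them.

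**Inputs**

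- Inclusion rule (sections 6.1, 7.2, 7.5.2): eligible if SCQ ≥ 15.
- Withdrawal rule as written (section 7.7): withdrawn and out of ITT if SCQ > 15.
- Candidate correction: withdrawn and out of ITT if SCQ < 15.

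**Comparison for whole-number scores around the threshold**

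| SCQ score | Eligible (≥ 15) | Withdrawn as written (> 15) | As written | Withdrawn if < 15 | With < 15 |
|---|---|---|---|---|---|
| 12, 13, 14 | no | no | conflict: ineligible, not caught | yes | coherent |
| 15 | yes | no | coherent | no | coherent |
| 16, 17, 18 | yes | yes | conflict: eligible and withdrawn | no | coherent |

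**Result as written.** A child who is both eligible (≥ 15) and not withdrawn (not > 15, that is, ≤ 15) must score exactly 15. Every higher score meets both rules at once, and every lower score meets neither.

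**Result with the sign reversed.** SCQ < 15 is the exact complement of SCQ ≥ 15, with no overlap and no gap.

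**A near miss to avoid.** Writing ≤ 15 would not be coherent, because a child scoring exactly 15 is eligible under the three entry statements and would then be withdrawn.

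**Is an upper limit intended?** Nothing in the protocol gives a reason for one. The amendment history entry on withdrawing ineligible children refers only to the missing diagnosis and says nothing about the SCQ.

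**The case against.** The strongest reply is that nobody could apply this rule by mistake. The SCQ phrase only illustrates what ineligible means, and eligibility itself is defined in section 6.1 and repeated in sections 7.2 and 7.5.2. Followed literally, section 7.7 would withdraw almost every child the trial recruits, so staff and statisticians would read it as <15. This stands as far as practical consequences go. It does not make the sentence correct, and a rule on who enters the ITT analysis should not depend on readers repairing it.

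A reader might infer three stronger points, none of which the protocol supports.

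- **That the ITT set would be nearly emptied of eligible children and filled with ineligible ones.** The first half is the literal reading, but it is not a credible outcome for the reason just given. The second half does not follow: children scoring below 15 are already refused entry under sections 7.2 and 7.5.2, so they should not reach the ITT set whatever section 7.7 says.
- **That the rule has no time limit, so that randomised children would be dropped and the randomised comparison broken.** The sentence is tied to ineligibility found when baseline data are taken. Section 7.4.1 places randomisation after eligibility has been established and baseline measures collected, and section 7.5.2 has the parent complete the SCQ before the baseline measures. The school record of the diagnosis is itself part of the inclusion criterion in section 6.1. If these steps are followed, a child removed under this rule has not been randomised. It may seem odd to mention ITT for such a child, but that does not extend the rule past baseline.
- **That ineligibility would be looked for harder in the intervention arm.** No section describes eligibility checks after allocation, so this would be speculation.

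**Conclusion.** The contradiction is real and can be verified from the protocol alone. Section 7.7 reverses the SCQ inequality against three consistent statements elsewhere, and only a score of exactly 15 satisfies both rules.

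The number of children affected depends on how the sentence is read. If staff apply the intended rule, as is likely, it is none. On the literal reading it is every eligible child scoring 16 or more, that is, the planned 240 less those scoring exactly 15. The protocol gives no SCQ distribution, so that group cannot be counted.

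The point is an internal inconsistency in an operative rule. It is not a flaw in the design: the intended population, the sample size and the randomised comparison are untouched. This rests on two assumptions: that the three matching statements express the intended threshold, and that baseline precedes randomisation as section 7.4.1 sets out.

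**What to change.** In section 7.7, change >15 to <15, so that the ground for withdrawal and exclusion from ITT is the exact complement of the inclusion rule in sections 6.1, 7.2 and 7.5.2. Do not use ≤ 15. If a statistical analysis plan restates this exclusion, its wording should be checked against the corrected sentence.

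The cost is a one-character correction, which can go into the next protocol amendment with an entry in the amendment history. No additional analysis is needed.
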